## 4.2. Scientific Rationale for Study Design

The current study has been designed to address regulatory guidance for FTIH studies in particular General Considerations for Clinical Trials [The International Council for Harmonisation of Technical Requirements for Pharmaceuticals for Human Use (ICH) E8/ Committee For Proprietary Medicinal Products ([CPMP/ICH/291/95](#)) and Guideline on Strategies to Identify and Mitigate Risk for First time in -Human Clinical Trials with Investigational Medical Products [[EMEA/CHMP/SWP/28367/07](#)] including participant selection, estimation of starting dose, precautions that are applied within and between dosing cohorts, dose escalation scheme, risk mitigation, and stopping rules.

This study represents the first administration of GSK3882347 in humans. The aim of the FTIH is to generate human safety, tolerability and pharmacokinetics of GSK3882347 in healthy participants. The study will be conducted in healthy adult participants comprising of healthy adult men and WONCBP.

Scheduled assessments of subjective symptoms, and objective clinical laboratory tests, vital signs, and 12-lead safety electrocardiograms (ECGs) will be obtained to monitor participant safety.

The single dose assessments in Part 1 will be conducted to determine safety, tolerability and pharmacokinetics of the study intervention in individuals before progressing to doses explored further in other parts of the study and will allow for any adjustments needed based on emerging safety, tolerability and PK data. Part 1 will also include the evaluation of the effect of food on GSK3882347.

Part 2 of this study is planned to include 7 days of repeat dosing to provide sufficient safety, tolerability, and PK as this is the anticipated dosing duration which will be used in females with recurrent UTI (rUTI). The dosing duration may be adjusted depending on PK data collected in Part 1 of the study.

Preclinical studies following oral administration as a suspension to rat and mini-pig, demonstrated that bioavailability was moderate (~40%) suggesting incomplete absorption of compound from the GI tract since first pass hepatic extraction was predicted to be low.

Bioavailability in the female rat following IP administration, which bypasses the GI tract, but not the liver, was ~75%, further supporting this supposition. The solubility in FeSSIF (Fed-state simulated intestinal fluid, pH 6.5) was significantly higher than solubility observed in SGF (simulated gastric fluid) and FaSSIF (Fasted-state simulated intestinal fluid). The concentration in FaSSIF is 0.4 to 0.5 mg/mL. The FeSSIF solubility was higher than the experimental maximum (1.13 mg/mL); therefore, the maximum solubility achievable in GI fluids is not yet known.

Following review of safety, tolerability, and pharmacokinetic data in Part 1, the food effect dose of GSK3882347 will be selected based on an assessment of the ongoing data from the prior single ascending doses. The formulation used for this study will be a capsule of GSK3882347 prepared by extemporaneous compounding. The preliminary results will be used to determine whether an effect of food on GSK3882347 can be anticipated in future studies which will utilise a tablet formulation and will help to guide the pivotal food effect study and commercialization [DHHS, 2019].

Current preclinical data and dose predictions do not indicate any cardiovascular risk. The study will evaluate the exposure-response relationship between GSK3882347 and QTcF as a possible alternative to conducting a thorough QT/QTC study [DARPO, 2014]. ECG wave forms will be collected in both parts and stored for potential analysis, depending on observed PK and other project considerations. The food effect in Part 1 will not be part of the cardio-dynamic evaluation.

A definitive *in vitro* study using human hepatocytes revealed that GSK3882347 was moderate inducer of CYP3A4. Based on the *in vitro* data and using preliminary risk assessments, GSK3882347A has the potential to perpetrate DDIs when co-dosed with CYP3A4 substrates, including oral contraceptives (OCs), resulting in a potential loss of efficacy of OCs and other substrates. Therefore, plasma 4 $\beta$ -hydroxycholesterol, a potential *in vivo* marker of CYP3A4 enzyme activity will be measured within Part 2 (subset - not all cohorts). A comparison will be made between the ratio of 4 $\beta$ -hydroxycholesterol: cholesterol in plasma at baseline and on Day 8 (i.e. approximately 24 hours after the Day 7 dose) in order to assess potential changes in CYP3A4 enzyme activity following repeat dosing of GSK3882347. This information, combined with PBPK modelling, may help to better inform the risk of co-administering GSK3882347 with OCs in future clinical studies which may include women of childbearing potential.

#### **4.3. Justification for Dose**

Estimated human pharmacokinetics for GSK3882347 were generated using a physiologically based pharmacokinetic (PBPK) model that correlates plasma and urine exposures incorporating estimates of renal and non-renal clearance derived from single species scaling of observed *in vivo* male rat and dog data. The predicted human clearance of GSK3882347 using rat or dog data differed by approximately 10-fold, therefore, two separate predictions of likely human pharmacokinetics and exposure for GSK3882347 in plasma and urine were established for a 70 kg human.

The highest planned dose in this study is 900 mg, which, for the human exposure prediction based on dog PK, provides 1.8-fold coverage to the rat NOAEL, when dosed

once-daily repeat doses. The doses in the protocol may be amended based on emerging human safety and PK data, however the human exposure will remain below the rat NOAEL and ICHQ3 principles will be followed to ensure that any impurities present in the drug product remain at acceptable levels if dose levels above 900 mg are used.

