## Part 2: Repeat Dose Escalation in Healthy Adult Participants

Part 2 consists of a maximum of four ascending repeat-dose cohorts (Cohorts 3 to 6), each with 10 participants who will receive a single oral dose of GSK3882347 or placebo for 7 days. The earliest point at which Part 2 of the study will be initiated is once the single dose safety and preliminary PK data at an exposure that exceeds the daily exposure predicted at steady state for the Part 2 planned starting dose of 50 mg is demonstrated in Part 1. The planned starting dose of GSK3882347 in Part 2 is 50 mg administered as once daily Days 1 to Day 7. The dose is planned to increase in subsequent cohorts to 150, 500 and 900 mg. The starting dose and maximum dose may be changed based on clinical safety, tolerability and PK findings in Part 1 or earlier doses in Part 2 and consideration of the area under the concentration-time curve (AUC) from time zero to 24 hours after dosing (AUC[0-24]) and maximum plasma concentration (Cmax) exposures based on the no-observed-adverse-effect-level (NOAEL).

Participants who meet the criteria for study entry will be assigned to the current dose level and randomized to receive GSK3882347 or placebo in a 4:1 ratio before administration of study intervention on Day 1 in Part 2. As a safety precaution, cohorts will be split into two sub-cohorts to allow sentinel dosing. At each dose level (Cohorts 3-6), the first two participants will receive either GSK3882347 or placebo (one active and one placebo). Dosing of the remaining eight participants (seven active and one placebo) in that cohort will occur at least 120 hours later based on review of the safety data (e.g. vital signs, ECGs, clinical laboratory results and adverse events) by the Principal Investigator and sponsor Medical Monitor from all sub-cohorts of sentinel participants. The 120 hour timeframe was selected on the basis of available preclinical data, as GSK3882347 is anticipated to have reached steady-state by 120 hours, however this duration may be increased or decreased based on emerging PK data.

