#### **4.3.1. Starting dose**

A single dose of 50 mg of GSK3882347 has been selected as the first dose to be administered to humans. This starting dose is calculated to have a 48.3-fold NOAEL safety margin to the human AUC0-24 predicted based on the dog PK and a 251-fold safety margin to the human AUC0-24 predicted based on the rat PK ([Table 5](#) and [Table 6](#)). An 81.0-fold NOAEL safety margin to the human Cmax is predicted based on the dog PK and a 205-fold safety margin is predicted using the rat PK ([Table 5](#) and [Table 6](#)).

Margins to the rat GLP toxicity study NOAEL are presented as the systemic exposure was lower in the rat as compared to the dog at the NOAEL (most conservative approach). The NOAEL in the 14-day GLP rat toxicity study was the top dose of 450 mg/kg/day and was associated with an AUC0-24,ss of 193  $\mu\text{g}^*\text{h}/\text{mL}$  and Cmax of 16.2  $\mu\text{g}/\text{mL}$ . As GSK3882347 does not have a human target, the Minimal Anticipated Biological Effect Level (MABEL) in humans for GSK3882347 could not be calculated.

The planned doses for dose escalation in Part 1 after dosing the first cohort with 50 mg are 150, 250, 500, 750, and 900 mg. Following each dose, the systemic PK (up to 24h post-dose) and safety data will be evaluated. The systemic exposure, Cmax and AUC (up to 24h) (where data permits) will be calculated for the current dose and predicted for the next dose level assuming linear PK. The predicted Cmax and AUC will be compared with the NOAEL from the rat and dog preclinical toxicology studies. The proposed dose for the next cohort may be modified if necessary; increments will be no greater than 3.5-fold.

**Table 5 Predicted Human AUC0-24 and Cmax Safety Margins Following Single and Multiple Dose Administration of GSK3882347 (Predicted Human PK Based on Dog PK)**

Dose (mg) §	Predicted human AUC 0-24 (μg*h/mL) #	Safety fold cover for AUC*	Predicted human C max (μg/mL)	Safety fold cover for C max *
SAD				
900	40.5	4.77	1.94	8.34
750	38.0	5.08	1.80	9.00
500	32.0	6.03	1.60	10.1
250	19.0	10.2	0.96	16.9
150	11.8	16.4	0.60	27.0
50	4.00	48.3	0.20	81.0
MAD				
900 QD	107	1.80	4.97	3.26
500 QD	80.0	2.41	3.70	4.38
150 QD	26.5	7.29	1.28	12.7
50 QD	8.87	21.8	0.43	37.7

§ Predicted efficacious exposure 50 mg (based on 5 μM target) and 300 mg (based on 30 μM target).

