### 7.1.5. Dose Adjustment/Discontinuation Pharmacokinetic Criteria

The exposures observed in animal toxicology studies will be used to guide dose escalation. Systemic exposures in the human participants in this study may exceed the systemic NOAEL animal exposures from 14-day GLP toxicology studies if the doses administered in the study are safe and well tolerated.

For Part 1, the need to dose escalate will be evaluated if no meaningful increase in exposure is observed with an increase in dose (i.e., a plateau in exposures is reached).

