### **8.4. Treatment of Overdose**

For this study, any dose of GSK3882347 greater than 900 mg within a 24-hour time period ( $\pm 1$  hour) will be considered an overdose.

Sponsor does not recommend specific treatment for an overdose.

In the event of an overdose, the investigator should:

- Contact the Medical Monitor immediately.
- Closely monitor the participant for AE/SAE and laboratory abnormalities until GSK3882347 can no longer be detected systemically (at least 5 days).
- Obtain a plasma sample for PK analysis if requested by the Medical Monitor (determined on a case-by-case basis).
- Document the quantity of the excess dose as well as the duration of the overdosing in the CRF.

Decisions regarding dose interruptions or modifications will be made by the investigator in consultation with the Medical Monitor based on the clinical evaluation of the participant.

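### Section 4.3 caps human exposure at the rat NOAEL, while Section 7.1.5 allows exposure above it, and the protocol does not say which rule governs

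*Protocol*

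**What the plan says.** Section 4.3 (Justification for Dose) gives the top planned dose as 900 mg and reports 1.8-fold cover to the rat NOAEL for repeat dosing on the dog-based prediction. It lets doses be amended on emerging data and foresees levels above 900 mg, with one limit stated without any condition: "however the human exposure will remain below the rat NOAEL".

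Section 4.3.1 (Starting dose) identifies that NOAEL. It is the top dose of the 14-day GLP rat study, with steady-state AUC(0-24) of 193 µg·h/mL and Cmax of 16.2 µg/mL. The rat was used because "the systemic exposure was lower in the rat as compared to the dog at the NOAEL". For Part 1 escalation, exposure is to be "predicted for the next dose level assuming linear PK" and compared with the rat and dog NOAELs.

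Section 7.1.5 (Dose Adjustment/Discontinuation Pharmacokinetic Criteria) opens with "The exposures observed in animal toxicology studies will be used to guide dose escalation". It continues: "Systemic exposures in the human participants in this study may exceed the systemic NOAEL animal exposures from 14-day GLP toxicology studies", on condition that the doses are safe and well tolerated. The next paragraph begins "For Part 1, the need to dose escalate will be evaluated if no meaningful increase in exposure is observed".

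On Part 2, the Synopsis says: "The starting dose and maximum dose may be changed based on clinical safety, tolerability and PK findings in Part 1", or on earlier Part 2 doses, with NOAEL-based exposures taken into consideration.

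**The concern.** An exposure ceiling is one of the main safeguards in a first-in-human study, and here the same protocol both sets it and waives it. If exposure runs well above prediction and the drug is well tolerated, a Dose Escalation Committee member relying on Section 4.3 would refuse the next dose level, while one relying on Section 7.1.5 could approve it. Both would be following the protocol. The Section 7.1.5 permission also has no upper bound of its own. The Part 2 maximum dose may be changed on emerging PK, so the situation can arise within the study as designed.

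**Working it through.** **Do the two sections use the same benchmark?** Section 4.3 refers to the rat NOAEL. Section 7.1.5 refers to NOAEL exposures from the 14-day GLP studies. Section 4.3.1 states that the rat NOAEL comes from such a study and is the lower in exposure of rat and dog. Exceeding either species' NOAEL exposure therefore means exceeding the rat's, and a species distinction does not reconcile the sections.

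**Is the permission confined to Part 1?** No. The words limiting a statement to Part 1 open the following paragraph, which concerns a plateau in exposure. The permission sentence speaks of participants in the study as a whole.

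**Does another section settle it?** The Synopsis only asks that NOAEL-based exposures be considered, and Section 4.3.1 only that predictions be compared with them. Sections 4.3.4, 6.6, 7.2 and 9.5.1 set no exposure cap.

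**Reproducing the stated margins** (NOAEL exposure ÷ predicted exposure, Tables 5 and 6):

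| Setting | Calculation | Margin |
|---|---|---|
| 900 mg single dose, dog-based AUC | 193 / 40.5 | 4.77 |
| 900 mg once daily, dog-based AUC | 193 / 107 | 1.80 |
| 900 mg once daily, dog-based Cmax | 16.2 / 4.97 | 3.26 |
| 900 mg once daily, rat-based AUC | 193 / 9.48 | 20.4 |

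These agree with the protocol.

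**When would the conflict bite?** Take the planned Part 2 step from 500 to 900 mg once daily and find the observed 500 mg mean at which projected 900 mg exposure reaches the limit. Section 4.3.1 states linear projection for Part 1 only, so using it in Part 2 is an assumption. The alternative uses the less-than-proportional rise in Table 5 (107/80 = 1.3375 for AUC).

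| Measure at 500 mg once daily | Linear projection | Table 5 or 6 shape |
|---|---|---|
| AUC, dog-based prediction 80 | 193 × 500/900 = 107.2; 107.2/80 = 1.34 | 193/1.3375 = 144.3; 144.3/80 = 1.80 |
| Cmax, dog-based prediction 3.70 | 16.2 × 500/900 = 9.0; 9.0/3.70 = 2.43 | 16.2 × 3.70/4.97 = 12.06; 12.06/3.70 = 3.26 |
| AUC, rat-based prediction 6.87 | 107.2/6.87 = 15.6 | 193 × 6.87/9.48 = 139.9; 139.9/6.87 = 20.4 |

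Below an observed mean AUC of about 107 µg·h/mL neither projection reaches the limit; above about 144 both do. AUC binds before Cmax. For example, an observed mean of 150 projects to 150 × 1.8 = 270 (linear) or 150 × 1.3375 = 200.6 (Table 5 shape). Section 4.3 would bar 900 mg once daily and Section 7.1.5 would allow it.

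**The case against.** The strongest reply is that the sections do different jobs. Section 4.3 limits how doses may be chosen in advance. Section 7.1.5 sits in the discontinuation section and may mean only that an observed excess is not in itself a reason to stop. That reading is possible, but the text does not state it, and the sentence follows directly on one about guiding dose escalation.

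A second reply is that intent is clear. The Amendment 2 entry in Appendix 10 records that exposure limits were added to Section 4.3, in response to the regulator, to define the highest permitted dose in exposure terms. This is good evidence that Section 4.3 is the intended rule. It is not a precedence clause, and the current Section 7.1.5 still grants the permission.

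Third, other controls exist: increments of at most 3.5-fold, no Part 2 dose above the Part 1 top dose, sentinel dosing, committee review, adverse-event stopping rules, and the overdose definition in Section 8.4 ("any dose of GSK3882347 greater than 900 mg within a 24-hour time period"). NOAEL exposures must also be considered or compared at escalation. These reduce the risk, but none is a binding exposure limit. The Dose Escalation Plan, which is not at hand, might address the point, but neither Section 4.3 nor Section 7.1.5 defers it there.

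Finally, the practical reach is modest, and this stands. No breach is predicted at any planned dose. The trigger requires exposure above the more pessimistic of two predictions. The rat NOAEL was the highest dose tested in that study, so 193 µg·h/mL is not a known toxicity threshold.

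**Conclusion.** The contradiction is real and should be fixed. One section forbids exposure above the rat NOAEL without condition, another permits it if the drug is tolerated, and no text ranks them. Predicted typical exposure stays below the limit throughout, with the smallest margin 1.80-fold (AUC at 900 mg once daily, dog-based). The rules would give different answers for the 900 mg once-daily cohort if mean AUC at 500 mg once daily came out 34% to 80% above the dog-based prediction. The lower figure assumes linear projection carries over to Part 2; the upper assumes the dose–exposure shape of Table 5. If human PK resembles the rat-based prediction, the limit is not approached.

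**What to change.** Delete the permission sentence in Section 7.1.5; that alone removes the conflict. Alternatively, replace it with wording such as: *Dose selection is subject to the exposure limit in Section 4.3: no dose level will be given whose predicted mean AUC(0-24) or Cmax exceeds the rat NOAEL values (193 µg·h/mL; 16.2 µg/mL).*

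The replacement has the added benefit of settling that the limit applies to predicted mean exposure, which Section 4.3 leaves open. If an observed excess is not meant to trigger stopping by itself, that can be stated separately without loosening the dose-selection limit.

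The change is one sentence, with no extra participants, samples or procedures. The only cost is less freedom to escalate when exposure is high and the drug is well tolerated, a freedom Section 4.3 already gives up.

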#### **4.3.1. Starting dose**

A single dose of 50 mg of GSK3882347 has been selected as the first dose to be administered to humans. This starting dose is calculated to have a 48.3-fold NOAEL safety margin to the human AUC0-24 predicted based on the dog PK and a 251-fold safety margin to the human AUC0-24 predicted based on the rat PK ([Table 5](#) and [Table 6](#)). An 81.0-fold NOAEL safety margin to the human Cmax is predicted based on the dog PK and a 205-fold safety margin is predicted using the rat PK ([Table 5](#) and [Table 6](#)).

Margins to the rat GLP toxicity study NOAEL are presented as the systemic exposure was lower in the rat as compared to the dog at the NOAEL (most conservative approach). The NOAEL in the 14-day GLP rat toxicity study was the top dose of 450 mg/kg/day and was associated with an AUC0-24,ss of 193  $\mu\text{g}^*\text{h}/\text{mL}$  and Cmax of 16.2  $\mu\text{g}/\text{mL}$ . As GSK3882347 does not have a human target, the Minimal Anticipated Biological Effect Level (MABEL) in humans for GSK3882347 could not be calculated.

The planned doses for dose escalation in Part 1 after dosing the first cohort with 50 mg are 150, 250, 500, 750, and 900 mg. Following each dose, the systemic PK (up to 24h post-dose) and safety data will be evaluated. The systemic exposure, Cmax and AUC (up to 24h) (where data permits) will be calculated for the current dose and predicted for the next dose level assuming linear PK. The predicted Cmax and AUC will be compared with the NOAEL from the rat and dog preclinical toxicology studies. The proposed dose for the next cohort may be modified if necessary; increments will be no greater than 3.5-fold.

**Table 5 Predicted Human AUC0-24 and Cmax Safety Margins Following Single and Multiple Dose Administration of GSK3882347 (Predicted Human PK Based on Dog PK)**

Dose (mg) §	Predicted human AUC 0-24 (μg*h/mL) #	Safety fold cover for AUC*	Predicted human C max (μg/mL)	Safety fold cover for C max *
SAD				
900	40.5	4.77	1.94	8.34
750	38.0	5.08	1.80	9.00
500	32.0	6.03	1.60	10.1
250	19.0	10.2	0.96	16.9
150	11.8	16.4	0.60	27.0
50	4.00	48.3	0.20	81.0
MAD				
900 QD	107	1.80	4.97	3.26
500 QD	80.0	2.41	3.70	4.38
150 QD	26.5	7.29	1.28	12.7
50 QD	8.87	21.8	0.43	37.7

§ Predicted efficacious exposure 50 mg (based on 5 μM target) and 300 mg (based on 30 μM target).

# Predicted AUC0-24 at steady-state (SS) was used for the calculations of the MAD safety margins.

\* Safety margins calculated using the NOAEL determined based on the 14-day GLP rat toxicity studies as AUC0-24,ss of 193 μg\*h/mL and Cmax of 16 μg/mL at the dose of 450 mg/kg/day.

**Table 6 Predicted Human AUC and Cmax Safety Margins Following Single and Multiple Dose Administration of GSK3882347 (Predicted Human PK Based on Rat PK)**

Dose (mg) §	Predicted human AUC 0-24 (µg*h/mL) #	Safety fold cover for AUC*	Predicted human Cmax (µg/mL)	Safety fold cover for Cmax*
SAD				
900	8.61	22.4	0.73	22.3
750	8.12	23.8	0.68	23.8
500	6.64	29.1	0.57	28.3
250	3.76	51.3	0.36	45.1
150	2.29	84.3	0.23	70.1
50	0.77	251	0.08	205
MAD				
900 QD	9.48	20.4	0.81	19.9
500 QD	6.87	28.1	0.60	27.2
150 QD	2.32	83.2	0.23	69.2
50 QD	0.78	248	0.08	203

§ Predicted efficacious exposure 300 mg (based on 5 µM target) and 650 mg (based on 30 µM target).  
# Predicted AUC0-24 at steady-state (SS) was used for the calculations of the MAD safety margins.  
\* Safety margins calculated using the NOAEL determined based on the 14-day GLP rat toxicity studies as AUC0-24,SS of 193 µg\*h/mL and Cmax of 16.2 µg/mL at the dose of 450 mg/kg/day.

The United States Food and Drug Administration (FDA) guidance suggests calculating a human equivalent dose (HED), based on the NOAEL in the most sensitive or most relevant preclinical species, utilizing scaling factors that are based on differences in body surface area between species. The HED is converted to a maximum recommended starting dose (MRSD) in humans by dividing by a safety factor (default = 10). The safety factor may be adjusted depending on the pharmacology, toxicology, preclinical pharmacokinetics of the drug, or previous experience with compounds in the same pharmacologic/structural class. Using the rat NOAEL, the HED was calculated to be 73 mg/kg. With a safety factor of 10, the estimated MRSD in humans would be 438 mg for a 60 kg human. The MRSD dose is ~ 8.8-fold higher than our proposed initial dose of 50 mg [DHHS, 2005].

